Official Title:Comparison of Bolus Dosing of Methohexital and Propofol in Elective Direct Current Cardioversion

NCT04187196

Protocol ID: IRB00061732

IRB-Approved Date: 8/26/2020

Study Title: Comparison of bolus dosing of methohexital and propofol in elective DC cardioversion

Principal Investigator: [name], MPH

Co-Investigators: [name]; [name]

Sponsor/Funding Source: none

Key words: Atrial fibrillation; Cardioversion; Methohexital; Propofol; Deep sedation; Intravenous anesthetics

Background, Rationale and Context

Direct current cardioversion has been in clinical use since the 1960s for the treatment of both atrial fibrillation and atrial flutter to restore sinus rhythm.¹ By applying a QRS-synchronized current of energy through electrodes/pads placed on the chest wall, atrial arrhythmias can be reset and sinus rhythm restored. Direct current cardioversion (DCCV) is used in both a diagnostic and a therapeutic fashion in the management of atrial fibrillation (AF) and atrial flutter (AFL).² DCCV shocks are optimally delivered from electrodes in an anterior-posterior position, biphasic waveform, at high energy levels with a high acute success rate approaching 94-96%.^{3,4} Due to the amount of energy applied to the chest, a DCCV can be an uncomfortable procedure for patients who are awake. To minimize the discomfort and pain, short acting, deep-sedation agents are used.⁵ Different medication choices are available for sedation during this relatively brief procedure

Prior studies of deep sedation with anesthesia commonly compare propofol to other agents such as midazolam or etomidate. A recent review article evaluated randomized trials of the above medications concluded that propofol was the best option for use in DCCV when compared to the others.⁶ The authors concluded that the hypotension and respiratory depression associated with propofol was acceptable when compared to the increased recovery time and risk of myoclonus of midazolam and etomidate, respectively.

At our institution, a majority of DCCV are performed in the electrophysiology lab (EP lab). Sedation is delivered by either a CRNA under the supervision of an anesthesiologist, or by an EP lab RN under the direction of an electrophysiologist. The medication choice for sedation has traditionally been at the discretion of the supervising physician. The medication choices for sedation at our institution have historically been either propofol or methohexital. Each medication has specific properties and pharmacokinetics that affect duration of action, hemodynamic changes, and respiratory depression.⁷ Although these medications have been compared in other settings, such as during fracture and dislocation reduction in the ED,⁸ there are limited studies on the use of methohexital for sedation during cardioversion. The largest study was a cost effectiveness cohort study of 1,473 patient undergoing an elective cardioversion using methohexital dosing of 0.4-0.6 mg/kg.⁹ Although this was a cost effectiveness study, the safety and cost savings lead the authors to continue to use it for their cardioversions. To date there has been only one, small, randomized controlled trial comparing propofol and methohexital for DCCV.¹⁰ There were only 10 patients per group in this three group randomized

controlled trial. Although it found no significant difference in the mean arterial pressure or time to awakening, there was a trend to quicker recovery in the patients receiving methohexitol.

We intend to perform a randomized, open-blinded, prospective study to evaluate the timeliness and safety of DCCVs when using methohexitol when compared to the more often used propofol. If there is a significant reduction in time to recovery from induction, the use of methohexitol as compared to propofol can significantly decrease healthcare costs based on staff utilization and cost of medications.¹⁰

Objectives

Hypothesis:

We theorize that the use of methohexitol during cardioversion will result in a shorter time to effective sedation and time to full recovery when compared to the use of propofol. This will change how sedation is approached for elective cardioversions.

Primary Hypothesis:

1. The mean time to recovery from sedation during a cardioversion using methohexitol for sedation will be significantly shorter than the recovery time using propofol for sedation, as evidenced by a short time from initiation of induction to a score of 2 on the Ramsay Sedation Scale.
2. The mean time to a Ramsay score of 5-6 will be significantly shorter using methohexitol than the time to the same sedation level using propofol

Secondary Hypothesis:

1. There will be no significant increase in adverse events associated with the use of methohexitol when compared with propofol.

Methods and Measures

Design

We will perform a randomized, open-blinded, prospective study on all patients present for DCCV who meet inclusion criteria and consent to enrollment in the study. Patients will be randomized to sedation with bolus dosing of either propofol or methohexitol

Setting

This will be a single site study at a large academic medical center – Wake Forest Baptist Medical Center

Subjects selection criteria

- **Inclusion Criteria**

We will select all patients over the age of 18 who present to Wake Forest Baptist Medical Center for a direct current cardioversion for treatment of paroxysmal or persistent atrial fibrillation as well as atrial flutter.

- **Exclusion criteria**

Patients with sedation for transesophageal echocardiogram within 30 minutes of DCCV will be excluded. Hemodynamically compromised patients (as defined by hypotension <90/50 mmHg, altered mental status, shock, ischemic chest discomfort, or heart failure) will also be excluded.

Sample Size

We intend to randomize a total of 150 patients to either propofol or methohexitol

The following calculations have been used to establish the sample size for the full study

According to a study evaluating bolus dosing of propofol as outlined above, the time to recovery was 10.98 ± 2.51 min.¹¹

We will presume that a significant difference in time to recovery will be 2 minutes based on the average recovery time of 9 minutes when using methohexitol in a small randomized controlled trial utilizing bolus dosing.¹²

Estimated sample size for two-sample comparison of means

Null hypothesis: $m_1 = m_2$, where: m_1 is the mean value in population 1

m_2 is the mean value in population 2. Mean time to recovery from sedation with propofol is no different than mean time to recovery from sedation with methohexitol.

Alternative hypothesis: $m_1 \neq m_2$. Mean time to recovery from sedation with propofol is different than mean time to recovery from sedation with methohexitol

Assumptions:

Alpha = 0.05 (two-sided)

Power = 0.8

Effect size = difference in mean value of the outcome variable population 1 and population 2 = 2 minutes

Standardized effect size = effect size \div standard deviation = $2 \text{ min} \div 2.51 \text{ min} = 0.797$

Based on the above calculations we will need to review at least 50 patients in a 1:1 equal distribution between propofol and methohexitol. We will randomize 150 patients to ensure significance.

Intervention and Interactions

All patients presenting to the EP lab will be informed about the study and those who agree to participate will sign informed consent.

Clinical data will be collected from electronic medical records of Wake Forest Baptist Health (WakeOne, Muse). Data that are not available electronically be obtained from the patient and/or accompanying

family members. The following clinical data will be collected: name, age, MRN, gender, ethnicity, race, height, weight, BMI, sodium, potassium, calcium, creatinine, creatinine clearance by Cockroft-Gault method, magnesium, presence or absence of antiarrhythmic medications (Na Channel blocker, Beta Blocker, Potassium Channel Blocker, Calcium Channel Blocker, Digoxin), CHA2DS2-VASC score, HAS-BLED score, presence of Watchman device, type of anticoagulation, INR if on warfarin. In addition to this we will collect parameters from the most recent echocardiogram (<1 year): Left atrial (LA) diameter, LA volume index, LVEDV, LVESV, EF, presence of a pre-procedure TEE. We will include the following parameters from the clinical history: HTN, HFrEF (<50%), HFpEF (>50%), prior stroke, DM, COPD, thyroid disorder, smoking status, drinking history, ASA Status, and Arrhythmia type.^{13,14}

Using the randomization tool within REDCap, our secure data storage program, stratified by sex, ASA status, and presence or absence of HFrEF (EF <50%), patients will be randomized to boluses of either methohexitol or propofol. Methohexitol will be given at an initial dose of 0.5 mg/kg, followed by 10 mg every minute after 2 minutes, if adequate sedation is not achieved. Propofol will be given at an initial dose of 0.8 mg/kg followed by 20 mg every minute after 2 minutes, if adequate sedation is not achieved.^{9,15} The CRNA or anesthesiologist will draw up the pre-specified dose.

The modified Ramsay Sedation Scale (RSS) will be used to gage the level of sedation.¹⁶ There are six sedation levels, three for awake and three for asleep. Awake levels are: 1, the patient is anxious, agitated or restless; 2, the patient is cooperative, oriented, and tranquil; 3, the patient responds to verbal commands. Asleep levels are: 4, the patient has a brisk response to a light glabellar tap or loud auditory stimulus; 5, sluggish response; 6, no response.

The goal level of sedation will be a Ramsay Sedation Scale (RSS) level of 5 or 6, as evidence by either sluggish or no response to a glabellar tap or loud auditory stimuli, respectively.¹⁶ Due to differences in appearance of the medications (methohexitol is clear, and propofol is milky), blinding of the administering personnel will prove to be difficult. Blinding of outcome assessment will be achieved by obscuring both the syringe and the patient's arm from the person collecting the information as well as the patient.¹⁷ Data collection personnel will be equipped with a stopwatch as well as a laptop loaded with REDCap to effectively record all necessary predictor and outcome variables.

Baseline Oxygen supplementation at 4L by nasal cannula and saline administered via a peripheral IV will be available throughout the entire case. Self-adhesive pads will be placed in the antero-posterior position on the chest.³ The patient will be given the prespecified dose of sedative. Once adequate sedation is achieved the patient will receive 100 to 150 J shock for atrial flutter and 150 to 200 J shock using a QRS synchronized biphasic defibrillator and self-adhesive pads (Zoll R-Series Plus and Pro-Padz, Zoll Medical Corporation, Chelmsford, MA, USA). The protocol will allow for a maximum of 3 shocks. If the initial attempt at DCCV is unsuccessful, manual pressure to the anterior pad will be allowed.

A standard 12-lead electrocardiogram (ECG) will be obtained before sedation, and after recovery. A 12-lead rhythm strip will be obtained roughly 10 seconds prior to DCCV and 20 seconds after each DCCV. All tracings will be acquired at a paper speed of 25 mm/s and a scale of 10 mm/mV (GE MAC55, GE Healthcare, Chicago, IL, USA). During the procedure, monitoring of heart rate (HR), brachial systolic

blood pressure (SBP), diastolic blood pressure (DBP), mean arterial pressure (MAP) respiratory rate (RR) and oxygen saturation (SpO₂) will be measured through a mounted patient monitor (Phillips Intellivue MP5, Koninklijke Philips N.V, Amsterdam, Netherlands). The above parameters will be measured at induction, before the shock, and every minute after the shock for the first 10 minutes, 15 minutes, 20 minutes and 30 minutes.

The following time intervals for the procedure will be recorded in seconds: (T1) time from end of injection to loss of conscious [RSS 5-6]; (T2) Time to first shock; (T3) time to eyes opening [RSS 3]; (T4) Time the ability to answer simple questions of age and name [RSS 2]

Outcome Measures

The primary outcome to be measured will be (T4) the time from initiation of sedation to full recovery (RSS of 2) as evidenced by the ability to answer the questions “What is your name and what is your age?”¹⁶ We will start the timer at the initiation of induction.

Secondary time based outcomes will include: (T1) time from end of injection to loss of conscious [RSS 5-6]; (T2) Time to first shock; (T3) time to eyes opening [RSS 3]. Secondary hemodynamic outcomes will be vital status parameters (HR, SBP, DBP, MAP, RR, SpO₂) at induction, prior to first shock, then 1, 3, 5, 7, 9, 10, 15, 20, and 30 minutes after first cardioversion.

Procedural parameters measured will be: Number of DCCV, max energy used for successful DCCV, success of DCCV, dosage of medication (mg/kg), need for re-dosing.

Safety endpoints will be: evidence of bradycardia (HR <60 bpm), Hypotension (decrease in SBP ≥20%, hypoxemia (SpO₂ nadir <85%), need for advanced airway maneuvers (jaw thrust/chin lift, or bag mask ventilation), apnea (respiratory arrest ≥ 20 seconds), Severity of World SIVA averse sedation event.¹⁸

Patient experience endpoints will be measured after full recovery: recall of pain at injection site (visual analog scale, VAS)¹⁹, recall of anything unpleasant about the procedure (VAS). These are 100 mm lines that are anchored with “no pain” or “no distress” on one end and “worst imaginable pain” or “worst imaginable distress” on the other end. The patient will utilize the computerized VAS within REDCap to mark the appropriate level.

Variables

Predictor Variables: name, age, MRN, gender, ethnicity, race, height, weight, BMI, sodium, potassium, calcium, creatinine level, creatinine clearance, magnesium, CrCl by Cockcroft gault, presence or absence of antiarrhythmic medications (Na Channel blocker, Beta Blocker, Potassium Channel Blocker, Non-dihydropyridine CCB, digoxin), CHA₂DS₂-VASC score, HAS-BLED score, presence of Watchman, anticoagulation use: DOAC, Warfarin, ASA, Plavix, recent INR. Parameters from the most recent echocardiogram (<1 year): Left atrial (LA) diameter, LA volume index, LVEDV, LVESV, EF, pre-procedure TEE, Hypertension, congestive heart failure, stroke, diabetes, COPD, previous thyroid disorder, smoking status, alcohol use, ASA Status, Arrhythmia type (Atrial Fibrillation with RVR (HR >100 bpm), Atrial

Fibrillation with controlled VR (HR <100 bpm), Atrial Flutter with 2:1 block, Atrial Flutter with variable block), medication for sedation, final medication dose

Outcome variables: T1 time to LOC, T2 time to first shock, T3 time to eyes open, T4 time to recovery, HRinduction, HRshock, HR1, HR3, HR5, HR7, HR9, HR10, HR15, HR20, HR30, SBP (1,3...etc.), DBP (1,3...etc.), MAP (1,3...etc.), RR (1,3...etc.), SpO2 (1,3...etc.), NumCV, MaxEnergy, DCCVsuecess, MedDose(mg/kg), Redose,

Safety measures: Bradycardia, Hypotension, Vasopressor use, Hypoxemia, Jaw Thrust, Bag Mask, Invasive Airway, Apnea, SIVAsensitivity, PainVAS, UnpleasantVAS.

Analytical Plan

Continuous variables will be summarized with mean (standard deviation) or median (interquartile range) depending on the normality of the data and compared using student's t-test or Wilcoxon rank-sum test, respectively. Categorical variables will be summarized with counts (percent) and compared using chi-square tests. Multivariate linear regression analysis will be used to examine relationships further and adjust where necessary.

Potential Limitations:

Inability to double blind the treatment: due to the difference in appearance between methohexitol (clear) and propofol (milky) we are unable to blind the administrator of the medication. However the researcher collecting the information and the patient will be blinded to treatment allocation by obscuring the patient's arm from the patient and the sedation type from the data collector. The selection of energy will be determined prior to randomization and selection for medication.

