During the last 12 months, how often did you have 5 or more (males) or 4 or more (females) drinks containing any kind of alcohol in within a two-hour period? [That would be the equivalent of at least 5 (4) 12-ounce cans or bottles of beer, 5 (4) five ounce glasses of wine, 5 (4) drinks each containing one shot of liquor or spirits - to be provided by interviewer if asked.] Choose only one.	 Every day  5 to 6 days a week  3 to 4 days a week  two days a week  one day a week  2 to 3 days a month  one day a month  3 to 11 days in the past year  1 or 2 days in the past year

ASA Status

- ASA I Normal Healthy Patient: Healthy, non-smoking, no or minimal alcohol use
- ASA II Mild Systemic Disease: Mild diseases only without substantive functional limitations. Examples include (but not limited to): current smoker, social alcohol drinker, pregnancy, obesity ($30 < \text{BMI} < 40$), well-controlled DM/HTN, mild lung disease
- ASA III Severe Systemic Disease: Substantive functional limitations; One or more moderate to severe diseases. Examples include (but not limited to): poorly controlled DM or HTN, COPD, morbid obesity($\text{BMI} \geq 40$), active hepatitis, alcohol dependence or abuse, implanted pacemaker, moderate reduction of ejection fraction, ESRD undergoing regularly scheduled dialysis, history (>3 months) of MI,CVA, TIA, or CAD/stents
- ASA IV Severe Systemic Disease That Is A Constant Threat To Life: Examples include (but not limited to): recent (< 3 months) MI, CVA, TIA, or CAD/stents, ongoing cardiac ischemia or severe valve dysfunction, severe reduction of ejection fraction, sepsis, DIC, ARD or ESRD not undergoing regularly scheduled dialysis

Arrhythmia Type

- Atrial Fibrillation with RVR (HR>100 bpm)
- Atrial Fibrillation with controlled VR (HR < 100 bpm)
- Atrial Flutter with 2:1 Block
- Atrial Flutter with variable block

Randomization Form

Study ID _____

Randomization Form: To be filled out by Anesthesiology, Data Collector To be Blinded

Randomization Group

Methohexital
 Propofol

Total Dose Given (mg) _____

Total Dose per body weight _____

Extra Dosing Required?

Yes
 No

(Methohexital: 10 mg every minute after 2 min,
Propofol 20 mg every minute after 2 minutes)

Number of Extra Doses

1
 2
 3
 4
 5

Cardioversion Procedure

Study ID

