Date of Cardioversion

Timed events during cardioversion

Start Stopwatch when anesthesia announces bolus initiated. Hit lap button after each time event.

T1 - Time To LOC (RSS 5 or 6)

(MM:SS)

T2 - Time To First Shock

(MM:SS)

T3 - Time To Eyes Open

(MM:SS, may be to voice or touch)

T4 - Time To Recovery (Able to answer both "What is your name and what is your age?")

(MM:SS)

Vitals Measurements Prior To Induction

Heart Rate

SBP

DBP

MAP

Respiratory Rate

SpO2

Vitals Measurements Prior to First Shock

Heart Rate

SBP

DBP

MAP

Respiratory Rate

SpO2

Vitals Measurements 1 Minute After Shock

Heart Rate

SBP

DBP

MAP

Respiratory Rate

SpO2

Vitals Measurements 3 Minutes After Shock

Heart Rate

SBP

DBP

MAP

Respiratory Rate

SpO2

Vitals Measurements 5 Minutes After Shock

Heart Rate

SBP

DBP

MAP

Respiratory Rate

SpO2

Vitals Measurements 7 Minutes After Shock

Heart Rate

SBP

DBP

MAP

Respiratory Rate

SpO2

Vitals Measurements 9 Minutes After Shock

Heart Rate

SBP

DBP

MAP

Respiratory Rate

SpO2

Vitals Measurements 10 Minutes After Shock

Heart Rate

SBP

DBP

MAP

Respiratory Rate

SpO2

Vitals Measurements 15 Minutes After Shock

Heart Rate

SBP

DBP

MAP

Respiratory Rate

SpO2

Vitals Measurements 20 Minutes After Shock

Heart Rate

SBP

DBP

MAP

Respiratory Rate

SpO2

Vitals Measurements 30 Minutes After Shock

Heart Rate

SBP

DBP

MAP

Respiratory Rate

SpO2

Cardioversion Summary

Successful Cardioversion?

- Yes
- No

[figure not shown]
[figure not shown]
[figure not shown]
Number of Cardioversions

- One
- Two
- Three

Maximum Energy Used

- 50 J
- 100 J
- 125 J
- 150 J
- 200 J

Cardioversion Workflow

Addendum A

Patient Contact Script (v6.02.2020)

1. Contact Patients who have a scheduled cardioversion (found on the status board on epic)
2. Good [Morning, afternoon, evening] [Mr/Ms.] [Last name] My name is [[name]] I am currently working as a recruiter and data collector for our electrophysiologists.
3. At the Wake Forest Baptist [Heart and Vascular Center](#), our electrophysiologists work collaboratively with [cardiologists](#), [cardiothoracic surgeons](#) and other heart and vascular specialists to provide state-of-the-art therapies for patients with simple to complex arrhythmias. In addition, our electrophysiologists are heavily involved with the latest research and clinical trials in cardiac electrophysiology

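### The primary recovery time T4 depends on when the patient is questioned, and the readable plan sets no asker, first-ask time or repeat interval

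*Combined protocol and SAP*

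**What the plan says.** Outcome Measures defines T4 as the time from the start of induction to a Ramsay score of 2, shown by answering two questions, name and age. The Cardioversion Procedure form in the Appendix starts the stopwatch when anesthesia announces the bolus and asks for a lap at each event. For T3 (eyes open) its note reads "MM:SS, may be to voice or touch".

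On blinding, Intervention and Interactions says that the administering staff can hardly be blinded because the drugs look different. Outcome assessment is to be blinded by "obscuring both the syringe and the patient's arm from the person collecting the information as well as the patient". Potential Limitations repeats that collector and patient are both kept unaware of the arm, and gives the means as "obscuring the patient's arm from the patient and the sedation type from the data collector".

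On data entry, Intervention and Interactions equips the data collectors with a stopwatch and "a laptop loaded with REDCap to effectively record all necessary predictor and outcome variables". The Variables section lists "medication for sedation, final medication dose" among the predictors and "MedDose(mg/kg), Redose" among the outcomes. The Appendix puts the randomization group, total dose, dose per body weight and extra doses on a separate form, headed "Randomization Form: To be filled out by Anesthesiology, Data Collector To be Blinded".

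**The concern.** T4 has a defined start and a defined end event, but the end event is a response to a prompt. A patient who could answer at minute 8 and is first asked at minute 9 is recorded at minute 9. The recorded value therefore depends on the patient's state and also on the behaviour of whoever rouses and questions the patient.

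The anesthesia staff present know the arm. If one of them speaks to or touches the patient, or puts the questions, the blinded collector records accurately a time that an unblinded colleague has set. Hiding the syringe and arm from the collector does not address this. The protocol expects methohexital to be faster (Objectives; Expected Results), so any effect of expectation would tend to favour the study hypothesis. Prompt timing that was neither standardised nor recorded cannot be corrected in the analysis.

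**Working it through.** **1. What the readable text fixes for T4**

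| Element | Where | Specified? |
|---|---|---|
| Clock start | Outcome Measures; Cardioversion Procedure form | Yes |
| End event and the two questions | Outcome Measures; Cardioversion Procedure form | Yes |
| Who asks | – | Not in readable text |
| When asking starts | – | Not in readable text |
| How often it is repeated | – | Not in readable text |
| When, and by whom, voice or touch is used for T3 | – | Not in readable text |

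The Cardioversion Workflow is listed in the Appendix but has no readable content, and some figures near it are not shown.

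**2. The plan's own figure.** Inputs from Sample Size: difference 2 min, SD 2.51 min, two-sided alpha 0.05, power 0.80, allocation 1:1.

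n per arm = 2 × (1.960 + 0.842)² × (2.51 / 2)² = 2 × 7.85 × 1.575 = 24.7, so 25 per arm and 50 in total. This reproduces the stated minimum. The protocol will randomize 150, which is 75 per arm.

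**3. What a systematic timing shift would do (illustration).** The shift b is an assumption. Suppose there is no true difference and prompting moves one arm by b relative to the other.

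Standard error of the difference = 2.51 × √(2/75) = 0.410 min.

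Probability of two-sided p<0.05 = Φ(b/SE − 1.96) + Φ(−b/SE − 1.96).

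| Shift b | b/SE | Probability of p<0.05 |
|---|---|---|
| 0 | 0 | 5% |
| 15 s | 0.61 | 9% |
| 30 s | 1.22 | 23% |
| 45 s | 1.83 | 45% |
| 60 s | 2.44 | 68% |

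The larger sample gives no protection. At 25 per arm the standard error is 2.51 × √(2/25) = 0.710 min. A 30-second shift then gives b/SE = 0.70 and a probability of Φ(−1.26) + Φ(−2.66) = about 11%, against 23% at 75 per arm.

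**4. How prompting could produce such a shift (also an assumption).** If recovery falls at random between equally spaced prompts, the mean detection delay is half the interval. Asking every 1 min in one arm and every 3 min in the other gives delays of 0.5 and 1.5 min, a 1-min artefact, or half of the 2-min target. The same interval in both arms gives equal delays and no artefact.

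**5. Who enters drug and dose.** The laptop sentence and the variable lists, read together, would cover drug and dose. Dose would reveal the arm, since the initial doses are 0.5 and 0.8 mg/kg. But the variable lists do not say who enters each item, and the Randomization Form does: Anesthesiology. The readable Cardioversion Procedure form has no drug or dose field. The laptop sentence is therefore too broad, and no readable text states the REDCap access rights.

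**The case against.** The strongest reply is that the plan does protect assessment. Syringe, arm and sedation type are hidden from the collector, allocation and dose sit on a form that another team completes, and the wording of the questions is fixed. This stands, and it rules out a stronger reading. A reader might infer from the laptop sentence and the variable lists that the blinded assessor is told to enter drug and dose, and so that blinding of the primary outcome is not protected. The heading of the Randomization Form contradicts that.

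Second, a prompting rule may exist in the unreadable Cardioversion Workflow. This also stands, so the absence can be asserted only for the readable text.

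Third, an unspecified interval applied alike in both arms adds delay and noise but no bias, and nothing shows that staff would rouse one arm earlier. That is correct: bias needs behaviour that differs by arm. The form's note on T3 describes an acceptable stimulus and does not invite staff to use it at will. What remains is that nothing readable keeps the timing of stimulation and questioning with the blinded person, while people who know the arm are present.

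**Conclusion.** The point holds in a limited form. The readable plan leaves the asker and timing of the T4 questions open, and the stimulus for T3 untimed, so unblinded staff could influence the primary outcome despite a blinded collector. The size is unknown. The 23% for a 30-second shift assumes no true difference, the plan's SD, 75 analysed per arm and a shift constant across patients. It shows sensitivity and is not an estimate of actual bias. The sample size calculation is unaffected.

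The documents do not support saying that the plan assigns drug and dose entry to the blinded assessor, or that blinding is unprotected. On data entry, only a broad sentence needs to be aligned with the Randomization Form.

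**What to change.** **T4 and T3.** In Outcome Measures and on the Cardioversion Procedure form, state that the blinded data collector asks both questions, at one fixed interval (for example every 30 seconds) from a fixed time after the last shock, identically in both arms. State also that any earlier stimulation by staff for clinical need is recorded with its time and is not restricted. If the Cardioversion Workflow already contains such a rule, cite it in Outcome Measures instead. The first-ask time should be early enough that few patients could already have answered before it.

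**Data entry.** In Intervention and Interactions, exclude the Randomization Form fields from what the collector records, and set REDCap user rights so that the collector cannot open that form or the randomization tool. The collector may still complete the Demographics and Baseline Data forms, which carry no allocation data.

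**Cost.** A few sentences and a rights setting, with no extra patients or staff for the prompting rule. T4 would be resolved only to the prompt interval. With 30-second prompts and recovery uniform between them, the mean delay is 0.25 min in both arms. The added variance is 0.5²/12 = 0.021 min², which moves the SD from 2.51 to √(6.300 + 0.021) = 2.514 min. Repeated prompting may itself affect arousal, but the schedule would be the same in both arms.

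### The bradycardia endpoint (HR <60 bpm) has no baseline condition and does not separate readings before and after the shock, which can dilute a difference between the sedatives

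*Combined protocol and SAP*

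**What the plan says.** The safety list in Outcome Measures opens with "Safety endpoints will be: evidence of bradycardia (HR <60 bpm". Nothing there or under Variables requires a fall from baseline, limits the period, or says which readings feed the endpoint. The next item in the same sentence is a change from an earlier value: "Hypotension (decrease in SBP ≥20" percent.

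Heart rate is a secondary haemodynamic outcome, read "at induction, prior to first shock, then 1, 3, 5, 7, 9, 10, 15, 20, and 30 minutes after first cardioversion". Intervention and Interactions gives a denser schedule, with readings every minute for the first 10 minutes after the shock and then at 15, 20 and 30 minutes.

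All patients enter in atrial fibrillation or flutter. The Background cites a "high acute success rate approaching 94-96" percent for the shock. Rate-slowing drugs are recorded as predictors: "presence or absence of antiarrhythmic medications (Na Channel blocker, Beta Blocker, Potassium Channel Blocker, Non-dihydropyridine CCB, digoxin". They are neither an exclusion nor a stratification factor; the strata are sex, ASA status and HFrEF. No eligibility criterion sets a lower limit on heart rate, and one arrhythmia category is "Fibrillation with controlled VR (HR <100 bpm", also without a lower limit.

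The secondary hypothesis reads "There will be no significant increase in adverse events associated with the use of methohexitol when compared with propofol". The Analytical Plan compares categorical variables by chi-square test, and no margin is given.

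**The concern.** The hypothesis is about events associated with the sedative, but the definition would be met by three different things: a rate already below 60 before any drug was given, a slow rate that follows conversion, and a slow rate caused by the sedative. Only the third bears on the choice between the drugs.

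The first two form a background that is the same in both arms on average. A shared background narrows the observed risk difference and usually also adds variance, so the chi-square test becomes less able to see a drug effect. For a hypothesis that is supported by a non-significant result, that loss is not neutral. The published rate could also be read as sedation harm when part of it reflects the cardioversion.

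**Working it through.** **The plan's own figure.** The only sample-size calculation is for recovery time: difference 2 min, SD 2.51 min, two-sided alpha 0.05, power 0.80. Per arm, n = 2 × (1.960 + 0.842)² × (2.51/2)² = 2 × 7.849 × 1.575 = 24.7, so 25 per arm and 50 in total. This agrees with the Sample Size section. The point here does not touch it. The documents give no rate, sample size or power for bradycardia.

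**Which readings could count.** The Outcome Measures list has 2 readings up to the shock (induction and before the first shock) and 9 after it (1, 3, 5, 7, 9, 10, 15, 20 and 30 min), so 9 of 11 are post-shock. The schedule in Intervention and Interactions gives 10 + 3 = 13 post-shock readings out of 15. An any-reading rule has more chances to be met under the second schedule, so the set that counts needs stating.

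**Dilution.** Let d be the drug-related rate in an arm and b the background rate common to both arms, and assume the two are independent. Then:

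- observed rate in an arm = 1 − (1 − b)(1 − d)
- observed risk difference = (1 − b)(d₂ − d₁)

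Power is an exact enumeration of two binomials with 75 patients each (150/2). The test rejects when |p̂₁ − p̂₂| / √[p̄(1 − p̄) × 2/75] exceeds 1.96, which is the uncorrected chi-square at 0.05. All values of d and b are assumptions. For d = 5% v 20%:

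| Background b | Observed rates | Risk difference (points) | Risk ratio | Power |
|---|---|---|---|---|
| 0% | 5.0% v 20.0% | 15.0 | 4.00 | 83% |
| 5% | 9.75% v 24.0% | 14.25 | 2.46 | 66% |
| 10% | 14.5% v 28.0% | 13.5 | 1.93 | 53% |
| 20% | 24.0% v 36.0% | 12.0 | 1.50 | 36% |
| 30% | 33.5% v 44.0% | 10.5 | 1.31 | 27% |

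Example row, b = 20%: 1 − 0.80 × 0.95 = 0.24 and 1 − 0.80 × 0.80 = 0.36.

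A normal approximation gives 80%, 53%, 36% and 26% at b = 0, 10%, 20% and 30%, the same pattern.

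**Other assumed effects.** For 2% v 15%, power is 88% with no background, then 63%, 48%, 30% and 22% at 5%, 10%, 20% and 30%. For 5% v 15% it is 55% with no background and 19% at 20%. For 5% v 10% it is only 22% with no background at all.

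**The case against.** A reader might infer that the definition hides a real drug difference, or that the bradycardia rate will mostly describe cardioversion. The documents support neither. They give no bradycardia rate, no prevalence of rate-slowing drugs and no evidence that the two sedatives differ in their effect on heart rate. That a converted patient on such drugs may fall below 60 is a reasonable clinical premise, but no section states it. At a background of 5% the loss is moderate, and for modest drug effects 75 per arm is too few whatever the definition. All of this stands, and it limits the claim to possible dilution of unknown size.

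Nor is the signal confined to this endpoint. Heart rate at induction, before the shock and at each later time is an outcome compared in its own right, and the severity of World SIVA adverse sedation events is a separate safety endpoint. A pre-shock difference in mean heart rate would stay visible, and the split by period could be made from planned data. That stands too. But a comparison of means does not replace the named binary endpoint, and a window chosen after the data are seen is not prespecified.

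It is also too simple to say that dilution only serves the investigators. Expected Results anticipates fewer haemodynamic side effects with methohexital, and dilution works against showing that.

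Finally, a tempting repair is to count only events between induction and the first shock. The objection to that is sound. The window holds one scheduled reading after the bolus. Its length is T2, itself an outcome that may differ by arm. It would also drop early post-shock readings taken while patients may still be sedated, given the recovery times of about 9 and 10.98 minutes used in Sample Size.

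On the baseline point, the controlled-rate category is an arrhythmia label, not a bradycardia rule. The gap is that nothing says whether a rate already below 60 before the bolus, or persisting after it, counts.

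**Conclusion.** The point holds as a definitional gap in a secondary safety endpoint. As written, the rule can count slow rates that precede the bolus or follow from conversion, and these can dilute a drug difference toward the hypothesised result. The direction follows from a background that is equal in both arms and independent of the drug effect. If background and drug-related events never fell in the same patients, the risk difference would not shrink. The size cannot be fixed from the documents. Under the assumed 5% v 20%, the loss runs from 17 points of power at a 5% background (83% to 66%) to 56 points at 30% (83% to 27%). It is not established that a drug difference exists or that one would be missed. The primary outcome is unaffected. The change is worth making because it is cheap and must be settled before the data are examined by arm.

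**What to change.** Keep the protocol's 60 bpm threshold and keep the overall any-time rate as the main comparison. Then prespecify:

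1. An event must be new: pre-induction HR of 60 or more. Report by arm the number already below 60, so that the denominator is clear. This condition uses a value taken before the drug is given.
2. Which scheduled readings count, after reconciling the two post-shock schedules.
3. New HR <60 by arm in two separate rows: the reading before the first shock, and the post-shock readings.
4. Any split by cardioversion success as descriptive only, because success is a post-randomisation outcome.

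The Cardioversion Procedure form already has the pre-induction, pre-first-shock and post-shock heart rates and the success field. The cost is revised endpoint wording, one extra table and fewer events per row. The post-shock row still mixes drug and conversion effects, and the pre-shock row rests on a single scheduled reading, so neither should replace the overall comparison.
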